## INTRODUCTION

Ketamine is a non-competitive N-methyl-D-aspartate (NMDA)/glutamate receptor complex antagonist that decreases pain by diminishing central sensitization, hyperalgesia, and "wind-up" phenomenon at the level of the spinal cord (dorsal ganglion) and central nervous system (1). Ketamine administration in sub-dissociative doses (SDK) of 0.1-0.3 mg/kg in pre-hospital settings and in the ED results in effective pain relief in patients with acute traumatic and non-traumatic pain, chronic non-cancer and cancer pain, and in patients with opioid-tolerant pain by virtue of providing anti-hyperalgesia, anti-allodynia, and anti-tolerance (2-4). Two commonly utilized routes of of SDK administration in the ED include an intravenous route (intravenous push dose or short infusion) and intranasal route (5-11).

## **BACKGROUND AND SIGNIFICANCE**

In the situation when intravenous access is not readily available or unobtainable, and intranasal route is not feasible, another non-invasive route of ketamine administration such as inhalation via Breath-Actuated Nebulizer (BAN) is coming into the play. The BAN allows a controlled patient-initiated delivery of analgesics in titratable fashion (12). Nebulized administration of ketamine has been studied in the areas of acute postoperative pain management (post-intubational sore throat), in anesthesia (pre-medication for general anesthesia,) and in managing cancer pain, and status asthmaticus therapy (13-14). However, our research team has published a case series of 5 patients receiving nebulized ketamine for a variety of acute painful conditions and has recently completed a randomized double-blind trial of 120 adult patients that evaluated analgesic efficacy and safety of nebulized ketamine at three different dosing regimens for acute pain in the ED.

Currently, we are conducting two additional studies evaluating the role of nebulized ketamine in pediatric ED and pre-hospital arena.

## STUDY OBJECTIVES

To compare analgesic efficacy and rates of side effects of sub-dissociative dose ketamine at 0.3 mg/kg dose administered via intravenous route as a short infusion over 15 minutes to a 0.75 mg/kg dose of ketamine administered via breath actuated nebulizer to adult patients presenting to the ED with acute painful and exacerbation of chronic painful conditions.

#### **HYPOTHESIS**

In our study we hypothesize that intravenous sub-dissociative-dose ketamine of 0.3 mg/kg will provide better analgesia at 30 min post-medication administration in comparison to nebulized ketamine administered at 0.75 mg/kg. The primary outcome of this trial is the comparative reduction in participant's pain scores at 30 minutes post medication administration.

## STUDY DESIGN

**Subjects:** Patients 18 years of age and older presenting to the ED with acute and chronic painful conditions such as traumatic and non-traumatic abdominal, flank, back, musculoskeletal pain, headache, as well as exacerbation of chronic abdominal, musculoskeletal and neuropathic pain with a score of 5 or more on a standard 11- point (0 to 10) numeric rating scale and requiring parenteral analgesia as determined by the treating attending physician. Patients' screening and enrollment will be performed by study investigators and research assistants. All patients will be enrolled at various times of the day when study investigators will be available for patient enrollment and an ED pharmacist will be available for medication preparation

Eligibility Criteria: Patients 18 years of age and older presenting to the ED with acute and chronic painful conditions such as traumatic and non-traumatic abdominal, flank, back, musculoskeletal pain, headache, as well as exacerbation of chronic abdominal, musculoskeletal and neuropathic pain with a score of 5 or more on a standard 11- point (0 to 10) numeric rating scale. Patients will have to be awake, alert, and oriented to person, place, and time, and will be able to demonstrate understanding of the informed consent process and content. Patients also will have to demonstrate ability to verbalize the nature of any adverse effects they might experience as well as to express their pain severity by using the NRS.

**Exclusion Criteria:** Altered mental status, allergy to ketamine, pregnant patients, weight greater than 150 kg, unstable vital signs (systolic blood pressure <90 or>180 mm Hg, pulse rate <50 or >150 beats/min, and respiration rate <10 or >30 breaths/min), inability to provide consent, and past medical history of alcohol or drug abuse, or schizophrenia.

**Design:** This is a prospective, randomized, double-blind, double dummy trial comparing analgesic efficacy and safety of intravenous SDK administered at 0.3 mg/kg over 15 minutes to nebulized ketamine at 0.75 mg/kg administered via BAN to patients presenting to the ED of Maimonides Medical Center with acute and chronic painful conditions. Upon meeting the eligibility criteria, patients will be randomized into two study groups: IV SDK and Nebulized K-BA

**Data Collection Procedures:** Each patient will be approached by a study investigator for acquisition of written informed consent and Health Insurance Portability and Accountability Act authorization after being evaluated by the treating emergency physician and determined to meet study eligibility criteria. When English will not be the participant's primary language, a language-appropriate consent form will be used and non-investigator, hospital-employed, trained interpreters or licensed telephone interpreter will assist in acquisition of informed consent. Baseline pain score will be determined with an 11-point numeric rating scale (0 to 10), described to the patient as "no pain" being 0 and "the worst pain imaginable" being 10. A study investigator will record the patient's body weight and baseline vital signs.

The on-duty ED pharmacist will prepare either a breath-actuated nebulizer with a dose of 0.75 mg/kg or an infusion dose of IV SDK at 0.3 mg/kg in 100 ml normal saline bag according to the predetermined randomization list, which will be created in SPSS (version 24; IBM Corp, Armonk, NY) with block randomization of every 10 participants. All participants will receive a corresponding placebo in order to maintain double-dummy design: the subjects randomized to receive IV SDK will also receive nebulized saline via BAN, and the subjects receiving K-BAN will also receive an IV infusion of Normal Saline over 15 minutes. The medication will be delivered to the treating nurse in a blinded fashion who will set up an infusion pump with a run time of 15 minutes. The nebulization of active drug and placebo via BAN will have a minimum time of 5 min and maximum time of 15 min.

Study investigators will record pain scores, vital signs, and adverse effects at 15, 30, 60, 90, and 120 minutes. If patients reported a pain numeric rating scale score of 5 or greater and requested additional pain relief, intravenous morphine at 0.1 mg/kg will be administered as a rescue analgesic.

The preparing ED pharmacist, research manager, and statistician will be the only ones with knowledge of the study arm to which each participant would be randomized. Treating providers, participants, and the data collecting research team will be blind to the medication route received.

**Sample Size:** Assuming a greater improvement in pain score in the IV group of 1.3 points over the nebulized group, with a SD of 3.0 in both groups, we will need to enroll 67 patients per group (134 total) to have 80% power at alpha = 0.0465, for a one-sided z-test. To account for possible missing data the total sample size will be 150 patients (75 per group). A pre-planned interim data analysis will occur upon reaching a total of total of 60 patients (30 patients per group), and alpha = 0.0035 will be used to maintain overall power, this will make the overall alpha of the study 0.05.

**Expected Outcomes:** The primary outcome will include a comparative reduction of pain scores on numeric rating pain scale (NRS) between recipients of IV SDK and K-BAN at 30 minutes post-analgesic administration.

**SAE Reporting:** Any serious adverse event, requiring intervention, will be reported to the IRB within 24 hours of discovery by the research staff. Less serious adverse events will be reported within a week of discovery. There are known expected outcomes and side effects to the procedures and medications being received and these are the same risks/side effects as the standard of care – these will be reported if they are serious and require intervention.

Table 1: Patient Recruitment and Follow-up Assessment Flow-Chart

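### The overall alpha of 0.05 is the plain sum of the interim and final levels: a valid upper bound, but the actual error is about 0.048 and the final level is slightly stricter than needed

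*Combined protocol and SAP*

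**What the plan says.** All the relevant figures are in the Sample Size paragraph of STUDY DESIGN.

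- **Planned spread of pain scores:** "with a SD of 3.0 in both groups".
- **Final analysis:** "67 patients per group (134 total) to have 80% power at alpha = 0.0465, for a one-sided z-test".
- **Planned difference between the arms:** "Assuming a greater improvement in pain score in the IV group of 1.3 points over the nebulized group".
- **Enrolment:** "To account for possible missing data the total sample size will be 150 patients (75 per group").
- **Interim:** one look, at a "total of 60 patients (30 patients per group"), where "alpha = 0.0035 will be used to maintain overall power".
- **Overall level:** "this will make the overall alpha of the study 0.05".

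No group-sequential boundary or spending function is named, and the action to follow a significant interim result is not described. The Data Analysis paragraph of the same section gives P<.05 as the mark of significance. It mentions neither 0.0465 nor a one-sided test.

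**The concern.** Two test levels add up to the overall type I error only if the two tests can never both reject. Here they can: the interim patients are part of the final data set, so the two statistics are positively correlated and some false positives at the interim would also be false positives at the end. The sum counts these twice. The actual error is therefore below 0.05, and the final test could be run at a slightly higher level with the overall error still at 0.05.

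What is at stake is modest. The plan puts 67 per group at 80% power, and at 0.0465 that number falls just short. The sentence on the interim also says that its level maintains power, when an interim level of this kind controls the type I error. Since no boundary method is named, that sentence is the only account of why the levels were chosen.

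**Working it through.** **Inputs (all from Sample Size).** Difference 1.3, SD 3.0 in both groups, one-sided z-tests, interim level 0.0035 at 60 patients, final level 0.0465, 67 per group (134) for power and 75 per group (150) enrolled. The calculation assumes that the interim can declare efficacy at 0.0035.

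**1. The plan's own figures.**
- Overall alpha: 0.0035 + 0.0465 = 0.0500, so the stated value is the sum.
- Sample size: n per group = 2 × (SD/difference)² × (z for alpha + z for power)² = 2 × (3.0/1.3)² × (1.680 + 0.842)² = 67.7. This agrees with 67 to within one patient, although rounding up gives 68.
- Power of the final test alone at 67 per group: the expected z is 1.3 / (3.0 × √(2/67)) = 2.508, and P(Z > 1.680 − 2.508) = 79.6%. At 75 per group it is 83.5%.
- A two-sided test at 0.0465 would need 86 per group, so the plan's number does rest on a one-sided test.

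**2. Actual overall error.** The critical values are 2.697 (interim) and 1.680 (final). With equal variance per patient, the correlation between the two statistics is the square root of the information fraction. Overall error = 1 − P(Z1 < 2.697 and Z2 < 1.680) under the null.

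| Final number analysed | Information fraction | Correlation | Overall one-sided error |
|---|---|---|---|
| 134 | 60/134 = 0.448 | 0.669 | 0.0477 |
| 150 | 60/150 = 0.400 | 0.632 | 0.0479 |

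Twenty million simulated pairs for each case gave 0.0477 and 0.0478. With 134 patients, the difference from the sum, 0.0500 − 0.0477 = 0.0023, is the probability that both looks reject under the null, which the sum counts twice.

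**3. Final level for an overall error of exactly 0.05, with 0.0035 kept at the interim.** Solve 1 − P(Z1 < 2.697 and Z2 < c) = 0.05 for c.

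| Final number analysed | Final level | Required n per group | Power with interim, at 0.0465 | Power with interim, at solved level |
|---|---|---|---|---|
| 134 | 0.04887 | 66.4 | 79.8% | 80.4% |
| 150 | 0.04866 | 66.5 | 83.6% | 84.1% |

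At the solved level the required number rounds up to 67, so the plan's 67 per group and 80% power are then both true. For use in the trial the level should be rounded down: 0.0489 itself, at 60/134, gives 0.05003.

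**4. If the P<.05 in Data Analysis were applied to the final primary test.** A one-sided look at 0.0035 followed by a one-sided test at 0.05 gives an overall error of 0.0511 (134) or 0.0513 (150).

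**The case against.** The strongest reply is that nothing here is an error. An additive (Bonferroni) split is a recognised method. It holds the overall error at or below 0.05 whenever the interim falls: with these levels the one-sided error runs from 0.0492 at an information fraction of 0.1 down to 0.0465 at 0.9. Read as a maximum, the stated 0.05 is right. The stricter level is already built into the sample size, which was worked out at 0.0465. The shortfall at 67 per group is less than one patient per group, and 150 are to be enrolled. A fixed 0.0465 also needs no joint model and no knowledge of the final count, whereas the solved level moves with the numbers analysed.

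Most of this stands. A reader might infer that the error rate is inflated or miscontrolled. The documents do not support that, because the departure is on the safe side. A reader might also infer that the trial is underpowered or gives up meaningful power. That is not supported either: the gain is 0.5 to 0.7 percentage points, and power at 75 per group is already 83.5% for the final test alone. Nor do the documents show that the primary test will be judged at 0.05. The P<.05 statement comes in a sentence about percentage differences and confidence intervals, and Sample Size gives 0.0465 for the final test. The gap is that the Data Analysis paragraph does not say which level governs the primary comparison.

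The timing point is met by fixing the interim level and the calculation rule in advance. The solved level then depends on patient counts alone and not on outcomes. What remains is that the plan presents 0.05 as the level achieved rather than as a bound, and describes the purpose of the interim level wrongly.

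**Conclusion.** The point holds as a small, nearly costless refinement. The stated 0.05 is a valid upper bound, and the actual one-sided error is about 0.048. The final level could be about 0.0489 (60/134) or 0.0487 (60/150) instead of 0.0465. That moves 67 per group from just under the stated 80% power to just over it.

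This rests on four assumptions: the interim can declare efficacy at 0.0035; the 60 interim patients are all in the final analysis; both looks use the one-sided z-test of the Sample Size paragraph; and patient counts measure information. If the interim could not declare efficacy, the overall error would simply be the final level, 0.0465. No conclusion of the trial is put at risk by leaving the levels as they are.

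**What to change.** Keep 0.0035 at the interim and state whether efficacy may be declared there. Then choose one of two courses before any unblinded look.

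1. **Solve the final level.** Pre-specify that the final one-sided level is the one that brings the overall error to 0.05 under the joint normal distribution of the two looks, calculated from the numbers actually analysed and rounded down (about 0.0489 at 60/134, 0.0487 at 60/150, before that rounding).
2. **Keep 0.0465.** Describe 0.05 as an upper bound, with an actual error of about 0.048, and describe power at 67 per group as just under 80%.

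In either case, replace the reference to maintaining overall power with maintaining the overall type I error. Repeat the final level and its sidedness in the Data Analysis paragraph, and say which analyses its P<.05 applies to.

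The cost is a few sentences, plus a short calculation under the first course. No patients are added.
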